AUC _{last}	Area under the curve calculated from minute 0 to the last measurable plasma concentration
AUC _{0-2 hr}	Area under the curve calculated from 0 hour to the 2 hour plasma concentration
BP	Blood Pressure
BUN	Blood Urea Nitrogen
C	Celsius
CAD	Coronary artery disease
CDMS	Clinical data management system
CFR	Code of Federal Regulations
cm ²	Centimeter squared
C _{max}	Maximum observed plasma concentration
CPK	Creatinine phosphokinase
CRF	Case report form
CRO	Contract research organization
CTA	Clinical Trials Authorization
CTM	Clinical trial material
CVA	Cerebral vascular accident
dL	Deciliter
DMP	Data Management Plan
ECG	Electrocardiogram
F	Fahrenheit
FDA	US Food and Drug Administration
GCP	Good Clinical Practice
GGT	Gamma-glutamyltransferase
HDL	High-density lipoprotein
HIPAA	Health Insurance Portability and Accountability Act
HR	Heart rate
ICF	Informed consent form
ICH	International Conference on Harmonisation
IEC	Independent Ethics Committee
IHS	International Headache Society
IND	Investigational New Drug
IRB	Institutional Review Board

IXRS	Interactive Voice/Web Recognition System
J	Joules
Kg	Kilogram
LDH	Lactate dehydrogenase
LDL	Low-density lipoprotein
LOCF	Last Observation Carried Forward
M207	Intracutaneous Microneedle System (M207)
Mg	Milligrams
mITT	Modified Intent-to-Treat
mL	Milliliter
MM	Medical Monitor
NDA	New drug application
NSAID	Nonsteroidal anti-inflammatory drug
PCP	Phencyclidine
PE	Physical examination
PRSPB	Patch-related superficial punctate bruising
PV	Pharmacovigilance
RDC	Remote Data Capture
RR	Respiratory Rate
SAE	Serious Adverse Event
SAP	Statistical Analysis Plan
SC	Subcutaneous
SD	Standard deviation
SEM	Standard error of the mean
SNRI	Serotonin-norepinephrine reuptake inhibitors
SOP	Standard operating procedures
SSRI	Selective serotonin reuptake inhibitors
TEAE	Treatment-emergent adverse event
TIA	Transient ischemic attacks
T _{max}	Time to maximum concentration
TMF	Trial master file
U/L	Units per liter
U.S.	United States
WOCBP	Women of child-bearing potential
ZP	Zosano Pharma

PROTOCOL SYNOPSIS

TITLE	A Long-Term, Open-Label Safety Study to Evaluate the Safety of M207 (Intracutaneous Microneedle System) in the Acute Treatment of Migraine
SPONSOR	Zosano Pharma Corporation
CLINICAL PHASE	Phase 3, Open-Label Safety
INDICATION	Acute migraine (with or without aura) in adults
OBJECTIVES	
 • The primary objective of the study is to assess the long-term safety of 3.8 mg (administered as two 1.9 mg patches) of M207 for the acute treatment of migraine • The secondary objective of the study is to evaluate the efficacy of 3.8 mg (administered as two 1.9 mg patches) of M207 for the acute treatment of migraine
TRIAL DESIGN	Open-Label, Multicenter, Safety Study
INVESTIGATIONAL TREATMENT	M207 Intracutaneous Microneedle patch system, 3.8 mg administered as two 1.9 mg patches (to be worn for 30 minutes)
BLINDING	N/A
RANDOMIZATION	N/A
STUDY POPULATION	Adults who suffer from 2-8 migraine attacks per month on average
NUMBERS OF SUBJECTS	
Approximately 400 subjects will be screened to ensure up to 300 subjects are eligible to enter the two-week run-in period and approximately 250 subjects eligible for the treatment phase:
 
 • At least 150 subjects must complete the safety follow-up for six months • At least 50 subjects must complete the safety follow-up for one year
ELIGIBILITY	
Inclusion Criteria:
 
Subjects presenting with all of the following may be included in the study:
 
 1. Able to provide written informed consent 2. Women or men 18 to 75 years of age 3. Greater than 1 year history of episodic, migraine (with or without aura) with onset prior to 50 years of age. Diagnosis must comply with International Headache Society (IHS ICHD-3beta) diagnostic criteria.

Diagnostic criteria must include a history of at least five attacks not attributed to any other disorder that include all of the following criteria:

- a) Headache attacks lasting 4-72 hours (untreated or unsuccessfully treated)
 - b) Headache has at least two of the following characteristics:
 - (i) unilateral location
 - (ii) pulsating quality
 - (iii) moderate or severe pain intensity
 - (iv) aggravation by or causing avoidance of routine physical activity (e.g., walking or climbing stairs)
 - c) During headache at least one of the following:
 - (i) nausea and/or vomiting
 - (ii) both photophobia and phonophobia
4. Migraine history during the 6-month period prior to initial screening must include:
- a) at least 2 migraines per month
 - b) no more than 8 migraines per month
 - c) no more than 15 headache days per month
5. Women of child-bearing potential must not be pregnant, must agree to avoid pregnancy during the trial, and must use an acceptable double-barrier method of birth control (examples of methods include partner using condom, female using IUD, hormonal or non-hormonal contraceptive, diaphragm with spermicide, or contraceptive sponge) for the duration of the trial.
6. No significant ECG findings, defined by:
- a) ischemic changes defined as > 1mm of down-sloping ST segment depression in at least two contiguous leads,
 - b) Q-waves present in at least two contiguous leads,
 - c) clinically significant intra-ventricular conduction abnormalities (left bundle branch block or Wolf-Parkinson-White syndrome), or
 - d) clinically significant arrhythmias (e.g., current atrial fibrillation)
7. Able to understand and operate the electronic diary
8. Able to apply the demo study drug patches
9. In the opinion of the investigator, subject is willing to treat a minimum of 2 migraines per month with study medication and is willing to consistently perform eDiary completion for up to 12 months.
-

Exclusion Criteria:

Subjects presenting with any of the following **will not** be included in the study:

1. Contraindication to triptans
 2. Use of any prohibited concomitant medications within 10 days of the Run-in Period (See [Section 6.2.11](#) for list of prohibited concomitant medications prohibited for the duration of the study)
 3. Use of any prescription anti-coagulant including Pradaxa (dabigatran), Coumadin (warfarin sodium), Eliquis (apixaban), and/or Xarelto (rivaroxaban) within 30 days prior to screening and throughout the duration of the study.
 4. History of hemiplegic migraine or migraine with brain stem aura (formerly called basilar migraine)
 5. Participation in another investigational trial during the 30 days prior to the Run-in Period or during this study
 6. Diagnosis of cancer (other than non-invasive skin cancer) within the 5 years prior to the Run-in Period
 7. History of unstable psychiatric illness requiring medication changes or hospitalization in the 12 months prior to the Run-in Period
 8. Known allergy or sensitivity to zolmitriptan or its derivatives or formulations
 9. Known allergy or sensitivity to adhesives and/or titanium
 10. Planned participation in activities which cause inflammation, irritation, sunburn, lesions, and/or tattoos at the intended application site from two weeks prior to screening through the last day of study participation
 11. Use of greater than 5 doses of opioid or barbiturate containing medications in the 30 days prior to screening and/or who anticipate using more than 5 doses per month of these medications at any time during the study
 12. Women who are pregnant, breast-feeding or plan a pregnancy during this study
 13. Clinically significant liver disease (SGPT > 150 U/L; SGOT > 130 U/L or LDH > 750 U/L)
 14. History of coronary artery disease (CAD), coronary vasospasm (including Prinzmetal's angina), aortic aneurysm, peripheral vascular disease or other ischemic diseases (e.g., ischemic bowel syndrome or Raynaud's syndrome)
 15. Three or more of the following CAD risk factors identified during screening:
-

-
- a) Current tobacco use
 - b) Hypertension (systolic BP > 140 or diastolic BP > 90) or receiving anti-hypertensive medication for treatment of hypertension
 - c) Hyperlipidemia – LDL > 159 mg/dL and/or HDL < 40 mg/dL (or on prescribed anti-cholesterol treatment)
 - d) Family history of premature coronary artery disease (CAD) (< 55 years of age in male first degree relatives or < 65 years of age in female first degree relatives)
 - e) Diabetes mellitus
16. History of cerebral vascular accident (CVA), transient ischemic attacks (TIA), or seizures
 17. History of concurrent illness that requires hospitalization within the 30 days prior to the Run-in Period
 18. Any other household member currently participating in a M207 study or relatives of site staff
 19. Any reason to believe that compliance with the study requirements and completion of evaluations required for this study will not be possible
 20. Any language barrier that, in the opinion of the Investigator, would preclude communication or compliance with the study requirements
 21. History or current abuse or dependence on alcohol or drugs that in the opinion of the investigator would interfere with adherence to study requirements
 22. Any positive urine drug screen for phencyclidine (PCP), MDMA (ecstasy), cocaine, and/or methamphetamine(s)
 23. Any clinically relevant abnormal findings in the subject's medical history, physical exam, vital signs or laboratory tests that, in the opinion of the Investigator, may put the subject at risk

Eligibility Criteria for Study Treatment

To be eligible for Treatment, subjects must continue to meet all eligibility criteria for the study and the following criteria observed during the Run-in Period:

1. At least one qualifying migraine attack in the last 14 calendar days prior to Visit 3 (Day 1). The following constitutes a migraine that qualifies during the Run-in Period:
 - a. Headache has at least two of the following characteristics:
 - unilateral location
 - pulsating quality

- moderate or severe pain intensity
 - aggravation by or causing avoidance of routine physical activity (e.g., walking or climbing stairs)
- b. During headache at least one of the following:
- nausea and/or vomiting
 - both photophobia and phonophobia
2. No more than seven headache days (headache days include both qualifying migraines and/or other headache types) in the last 14 calendar days prior to Visit 3 (Day 1)
 3. During the run-in period, good eDiary compliance will be confirmed by subject eDiary completion of at least 10 out of the last 14 calendar days prior to Visit 3 (Day 1)
 4. Demonstrated ability to properly operate the eDiary
 5. Demonstrated ability to properly apply the demo study drug patches
 6. In the opinion of the investigator, subject is willing and able to treat all eDiary-confirmed migraines for up to 12 months with good eDiary completion compliance
 7. Confirmation of continuing good general health, or stable non-serious disease that in the opinion of the Investigator will not place the subject at risk

CENTERS	Multicenter in the United States
STUDY DURATION	1 week screening period, two-week (+ up to 1 week) run-in period, 6 to 12 month treatment period, and a two-week safety follow-up visit
EFFICACY ASSESSMENTS	
Headache symptoms at time of treatment, 30 min, 2 hour, 12 hour, 24 hour and 48 hours post patch application:
 
 • Pain severity (0 = none, 1 = mild, 2 = moderate, 3 = severe) • Most bothersome other symptom (present/absent) • Nausea (Absent/Present) • Photophobia (Absent/Present) • Phonophobia (Absent/Present) • Rescue medication use • Pain relief (present/absent) • Migraine recurrence • Migraine-ACT Questions (Assessment of Current Therapy)

**SAFETY
ASSESSMENTS**

- Subject-reported skin assessments 30 min, 2 hours, 12 hours, 24 hours and 48 hours
- Investigator skin assessment at all post-treatment visits
- Adverse Events
- Physical exam including height and weight
- Vital signs including blood pressure
- Clinical Laboratory determinations including serum chemistries and hematological parameters
- 12-lead ECGs
- Assessment of concomitant medications

**STUDY
PROCEDURES**

- Screening procedures may be performed in 1 to 7 days
- Run-in period for 2 (+ up to 1) weeks prior to Day 1
- Clinic visits include Screening, drug dispensation visit Day 1, Month 1, 2, 3, 6, 9, 12 (or early discontinuation)
- A minimum of 2 migraine attacks treated per month with subject skin assessment recordings at 30 minutes, 2 hours, 12 hours, 24 hours and 48 hours post patch application

**STATISTICAL
ANALYSES**

The safety population will include all subjects who received any amount of study drug (i.e., applied at least 1 patch). Adverse events will be summarized overall and by preferred term and system organ class. Adverse events will also be summarized by severity and relationship to study drug. Serious AEs and AEs leading to discontinuation of study drug will also be summarized. Actual values and changes from baseline for clinical laboratory test results and vital sign measurements will be summarized using descriptive statistics (n, mean, SD, median, minimum, and maximum). ECG parameters will be summarized using shift tables. The number and percentage of subjects experiencing Bruising, Erythema, and Edema and other skin assessments will be tabulated.

All efficacy endpoints will be summarized using descriptive statistics. Further details regarding efficacy analyses can be found in the statistical analysis plan.

TABLE OF CONTENTS

PROTOCOL SIGNATURE PAGE - PRINCIPAL INVESTIGATOR	2
LIST OF ABBREVIATIONS AND DEFINITION OF TERMS	3
PROTOCOL SYNOPSIS	5
TABLE OF CONTENTS	11
LIST OF TABLES	14
LIST OF FIGURES	14
1 INTRODUCTION	16
1.1 Background.....	16
1.2 Clinical Pharmacology, Efficacy, and Safety of Zolmitriptan.....	17
1.2.1 Human pharmacokinetics.....	17
1.2.2 CP-2016-001 Clinical Efficacy and Safety Study.....	19
1.2.2.1 Primary Efficacy Analysis.....	20
1.2.2.2 Secondary Efficacy.....	21
1.2.2.3 Previous Co-Primary Endpoints in Migraine Trials for Comparison.....	22
1.2.2.4 Safety Results.....	24
1.3 Study Rationale.....	28
2 STUDY OBJECTIVES	29
2.1 Primary Objective.....	29
2.2 Secondary Objectives.....	29
3 INVESTIGATIONAL PLAN	30
3.1 Study Design.....	30
3.2 Selection of Study Population.....	31
3.2.1 Number of Subjects.....	31
3.2.2 Inclusion Criteria.....	31
3.2.3 Exclusion Criteria.....	33
3.2.4 Eligibility Criteria for Study Treatment.....	35
3.2.5 Prior and Concomitant Medications Allowed During the Study.....	36
3.2.6 Early Termination.....	36
3.2.6.1 Withdrawal of Subjects.....	36
3.2.6.2 Replacement of Subjects.....	37

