7.3.2 Safety Analyses

Safety will be assessed by the monitoring and recording of AEs, clinical laboratory tests, vital signs, physical examination findings, ECG parameters, and Investigator and subject reported skin assessments.

All safety analyses will be based on the Safety Population. Adverse events will be coded using the current Medical Dictionary for Regulatory Activities (MedDRA) dictionary (using the latest version) and will be summarized overall and by preferred term and system organ class. Adverse events will also be summarized by severity and relationship to study drug. Serious AEs and AEs leading to discontinuation of study drug will also be summarized.

Actual values and changes from baseline for assessments of clinical laboratory test results, ECG parameters, and vital sign measurements will be summarized at each visit using descriptive statistics (n, mean, SD, median, minimum, and maximum) or shift tables as appropriate. The number and percentage of subjects experiencing Bruising, Erythema, Edema and other skin assessments will also be summarized.

All data gathered will be listed by patient and parameter, separate listings of all abnormal laboratory findings will be provided, and clinically significant abnormalities will be recorded as AEs.

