4.2. SAFETY ENDPOINTS

- Changes from baseline in physical examination findings at Months 6 and 12
- Changes from baseline in vital signs at Months 1, 2, 3, 6, 9, 12, and at the 2-week post-study visit
- Changes from baseline in clinical laboratory parameters at Month 12
- Changes from baseline and/or shifts in 12-lead ECG parameters at Months 6 and 12
- Frequency of concomitant medications

- Incidence of treatment-emergent systemic and skin AEs (TEAEs)
- Frequencies of type of redness, severity of swelling, amount of bruising, and amount of bleeding (30 minutes only) at the application site as reported by the subject at 30 minutes, 2 hour, 12 hour, 24 hour, and 48 hours post-dose
- Frequencies of amount of skin itching and severity of pain at the application site as reported by the subject at 48 hours post-dose
- Frequencies of amount of bruising, erythema, and edema at the application site as assessed by the Investigator at Months 1, 2, 3, 6, 9, 12, and at the 2-week post-study visit
- Proportion of subjects with presence of skin signs and symptoms as assessed by the Investigator at Months 1, 2, 3, 6, 9, 12, and at the 2-week post-study visit

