11. SAFETY

Safety will be assessed through the following:

- Physical examination findings including height (at screening and final visit only) and weight,
- Vital signs including blood pressure,
- Clinical laboratory determinations including serum chemistries and hematological parameters,
- 12-lead ECGs,
- Assessment of concomitant medications,
- All treatment-emergent systemic and skin AEs (TEAEs),
- Subject reported Skin Assessment, and
- Investigator Skin Assessment.

All safety analyses will be based on the Safety Population. Adverse events will be coded using the current Medical Dictionary for Regulatory Activities (MedDRA) dictionary (version 20.0 or higher) and will be summarized overall and by preferred term and system organ class. Adverse events will also be summarized by severity and relationship to study drug. Serious AEs and AEs leading to discontinuation of study drug will also be summarized.

Clinical laboratory test results and ECG parameters will be summarized at each visit using shift tables or listings of abnormal results as appropriate. The number and percentage of subjects experiencing Bruising, Erythema, Edema and other skin assessments will also be summarized.

All data gathered will be listed by patient and parameter, separate listings of all abnormal laboratory findings will be provided, and clinically significant abnormalities will be recorded as AEs.

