11.4. VITAL SIGNS

All subjects will have vital signs including body temperature (TEMP), respiratory rate (RR), systolic blood pressure (SBP), diastolic blood pressure (DBP) and heart rate (HR)

measured at screening and all subsequent visits. Weight will be collected at selected visits, and height will be collected at screening and final visit only (or early termination visit).

A listing of abnormal vital signs results will be provided using the ranges below. All vital signs measurements will also be listed for each subject.

Vital Sign	Low Cutoff	High Cutoff
Systolic Blood Pressure	90 mmHg	139 mmHg
Diastolic Blood Pressure	60 mmHg	89 mmHg
Heart Rate	50 beats/minute	100 beats/minute
Respiratory rate	12 breaths/minute	20 breaths/minute
Body Temperature	36.1 degrees Celsius	37.5 degrees Celsius

11.5. 12-LEAD ECG

Twelve-lead ECG will be performed at screening, months 6 and 12 study visits. Abnormal ECG results will be listed. All ECG findings collected in the CRF will also be listed.

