14.3.1.3a	Study Drug-Related Treatment Emergent Adverse Events by System Organ Class and Preferred Term - ALL Adverse Events Safety Set
14.3.1.3b	Study Drug-Related Treatment Emergent Adverse Events by System Organ Class and Preferred Term - E-Diary Skin Assessment Reported Adverse Events Safety Set
14.3.1.3c	Study Drug-Related Treatment Emergent Adverse Events by System Organ Class and Preferred Term - Other Subject Reported Adverse Events Safety Set
14.3.1.4	Serious Treatment Emergent Adverse Events by System Organ Class and Preferred Term-ALL Adverse Events Safety Set
14.3.1.5	Treatment Emergent Adverse Events of Special Interest by System Organ Class and Preferred Term- ALL Adverse Events Safety Set
14.3.1.6a	Treatment Emergent Adverse Events by Maximum Severity by System Organ Class and Preferred Term - ALL Adverse Events Safety Population
14.3.1.6b	Treatment Emergent Adverse Events by Maximum Severity by System Organ Class and Preferred Term - E-Diary Skin Assessment Reported Adverse Events Safety Population
14.3.1.6c	Treatment Emergent Adverse Events by Maximum Severity by System Organ Class and Preferred Term - Other Subject Reported Adverse Events Safety Population
14.3.2.1	Summary of Subject Reported Skin Assessment by Time After Patch Application Safety Population
14.3.2.2	Summary of Subject Reported Skin Assessment by Time After Patch Application - All Migraines Safety Population
14.3.2.3	Summary of Investigator Reported Skin Assessment by Visit Safety Population
14.3.2.4	Number of Treated Qualifying Migraines per Subject Safety Population
14.3.2.5	Number of Treated Qualifying Migraines per Month by Subject Safety Population
14.3.2.6	Number of Symptoms by Time Points - All Migraines Safety Population
14.3.3.1.1	Shift in Laboratory Tests: Hematology Safety Population
14.3.3.2.1	Shift in Laboratory Tests: Serum Chemistry Safety Population

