19. INDEX OF LISTINGS

Listing Number	Table Title
16.2.1	Subject Disposition Enrolled Population
16.2.2	Protocol Deviations Enrolled Population
16.2.3	Subject Enrollment and Screen Failures Screened Population
16.2.4.1	Demographics Enrolled Population
16.2.4.2	Migraine History Enrolled Population
16.2.4.3	Migraine Assessment of Current Therapy (Migraine ACT) Enrolled Population
16.2.4.4	Medical History Enrolled Population
16.2.4.5	Prior and Concomitant Medications Enrolled Population
16.2.5.1	Study Drug Accountability Enrolled Population
16.2.6.1	eDiary: Subject Reported Skin Assessment Safety Population
16.2.6.2.1	eDiary: Symptoms Safety Population
16.2.6.2.2	eDiary: Pain Data Safety Population
16.2.6.2.3	eDiary: Other Pre-Dose Symptoms Safety Population
16.2.6.2.4	eDiary: All Information Safety Population
16.2.6.3	Investigator Skin Assessment: Symptoms Safety Population
16.2.7.1	Adverse Events Safety Population
16.2.7.2	Serious Adverse Events Safety Population
16.2.7.3	Adverse Events Leading to Death Safety Population
16.2.7.4	Adverse Events Leading to Study Drug Termination Safety Population
16.2.8.1.1	Laboratory Tests - Hematology Screened Population
16.2.8.1.2	Laboratory Tests - Serum Chemistry Screened Population
16.2.8.1.3	Laboratory Tests - Other Tests Screened Population
16.2.8.1.4	Laboratory Tests - Drug Abuse Testing Screened Population
16.2.8.1.5	Laboratory Tests - Pregnancy Test Screened Population
16.2.8.2	ECG Interpretation Screened Population
16.2.8.3.1	Vital Signs Screened Population
16.2.8.3.2	Subjects with Abnormal Values of Vital Sign Parameters Screened Population
16.2.8.4	Physical Examinations Screened Population

Listing Number	Table Title
16.2.8.5	Fitzpatrick Skin Scale Screened Population
16.2.8.6	Current Alcohol Drug Use Screened Population
16.2.9.1	Monthly Phone Contact Screened Population

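### The Month 6 and Month 12 ECG endpoint has no planned summary table: the SAP provides only by-subject listings and does not declare this departure from the protocol

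*Protocol*

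**What the plan says.** The protocol makes the commitment in three places. The synopsis, under Statistical Analyses, says "ECG parameters will be summarized using shift tables". Protocol 7.1.1 names ECG changes or shifts at Months 6 and 12 as a safety endpoint. Protocol 7.3.2 says "ECG parameters, and vital sign measurements will be summarized at each visit using descriptive statistics", or by shift tables where these suit better.

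SAP 4.2 carries the endpoint over unchanged: "Changes from baseline and/or shifts in 12-lead ECG parameters at Months 6 and 12". The general text of SAP 11 adds an alternative that the protocol does not have: "Clinical laboratory test results and ECG parameters will be summarized at each visit using shift tables or listings of abnormal results as appropriate". SAP 11.5 gives the schedule, "Twelve-lead ECG will be performed at screening, months 6 and 12 study visits", and then the whole of the planned reporting: "Abnormal ECG results will be listed. All ECG findings collected in the CRF will also be listed".

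SAP 17 ends with two laboratory shift tables, one for hematology and the other titled "Shift in Laboratory Tests: Serum Chemistry Safety Population". The only ECG output in any index is Listing 16.2.8.2, "ECG Interpretation Screened Population". SAP 13, on changes from the protocol, covers efficacy endpoints only.

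**The concern.** The primary objective is long-term safety, and the ECG endpoint is one of the named safety endpoints that serve it. An endpoint defined as a change or shift from baseline needs an output that pairs each subject's baseline with the later reading and counts the result. A listing does not do that.

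Baseline matters here because an abnormal ECG does not by itself bar entry. Inclusion criterion 6 names particular or clinically significant findings, and protocol 6.2.10 excludes subjects with a clinically significant abnormality on the screening ECG as read centrally. A subject with a non-significant abnormality can be treated and will probably still show it at Month 6. If only abnormal results are listed, that subject looks the same as one whose ECG changed on treatment.

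At stake is whether the clinical study report can say how many treated subjects, out of how many with paired ECGs, had a new or worsened ECG finding after 6 or 12 months of repeated use.

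**Working it through.** No figure in the plan needs reproducing. The check traces the endpoint from commitment to output.

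| Place | What it provides for ECG |
|---|---|
| Protocol synopsis | Shift tables, without condition |
| Protocol 7.1.1 | Endpoint: change or shift at Months 6 and 12 |
| Protocol 7.3.2 | Descriptive statistics or shift tables |
| SAP 4.2 | Same endpoint |
| SAP 11 | Shift tables, or listings of abnormal results |
| SAP 11.5 | Two kinds of listing |
| SAP 13 | No ECG change declared |
| SAP 17 | No ECG table |
| SAP 18 | No ECG figure |
| SAP 19 | One ECG listing (16.2.8.2) |

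**Count of indexed tables (SAP 17).** Disposition, baseline and exposure 9; efficacy 9; adverse events 12; skin assessments and treated migraines 6; laboratory shifts 2. Total 9 + 9 + 12 + 6 + 2 = 38, of which 0 are for ECG. The index of figures has 3 entries, all on skin scores.

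**How laboratory tests fare under the same sentence.** SAP 11 treats laboratory tests and ECG together. For laboratory tests, SAP 11.3 goes on to specify low/normal/high shifts, and SAP 17 has the two tables. For ECG, SAP 11.5 specifies listings and SAP 17 has nothing. So the choice left open in SAP 11 has been settled as listings only.

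**What the listings allow.** SAP 11.5 lists all ECG findings, not just abnormal ones. ECGs are taken at screening, Month 6 and Month 12, and SAP 15.2.5.3 sorts listings by subject and then visit. A subject's screening ECG therefore appears with the later ones, and a shift can be read off by hand.

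**What they do not give.** Listing 16.2.8.2 is for the Screened Population. With about 400 screened and about 250 treated, some 400 − 250 = 150 subjects in it would never have been treated, whereas SAP 5.1 bases all safety analyses on the Safety Population. To answer the endpoint, a reader would have to remove the untreated subjects, pair the visits, classify each pair and count.

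**Illustration of scale (assumed rates; the documents give none).** Suppose 10–30% of treated subjects have a non-significant abnormal screening ECG that persists, that 3% of those normal at baseline become abnormal, and that 150–250 ECGs are available at Month 6. The upper figure of 250 ignores dropout.

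- Abnormal at Month 6 with no change from baseline: 150 × 0.10 = 15, up to 250 × 0.30 = 75.
- Newly abnormal: 150 × 0.70 × 0.03 = 3.2, up to 250 × 0.90 × 0.03 = 6.8.

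Under these assumptions, a listing restricted to abnormal results would consist mostly of unchanged subjects. The finding does not depend on these rates.

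**The case against.** A reader might infer that new ECG abnormalities cannot be told apart from pre-existing ones, or that the endpoint gets no result at all. The documents do not support either reading. All findings are listed with their screening values, so the distinction can be made subject by subject. Only the aggregate is missing.

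It can also be said that clinically significant ECG changes are counted elsewhere. Subjects with a clinically significant screening abnormality are excluded. SAP 11 says clinically significant abnormalities will be recorded as adverse events, and treatment-emergent events are tabulated. This stands in part. That clause follows directly on one about laboratory findings, and the explicit reporting rules for abnormal tests in protocol 8.2.1 cover laboratory tests only, although the general adverse event definition there is broad enough to include an ECG finding. Even if it applies, a shift from normal to abnormal but not significant stays uncounted, and an adverse event table does not use paired ECGs as its denominator.

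The clinical signal is also weak. Protocol 1.2.1 reports small blood pressure rises after dosing, but also no clinically meaningful ECG changes, and the Month 6 and Month 12 ECGs are not timed to a dose. This limits the urgency. It does not settle the question, because that study gave single administrations to 20 healthy volunteers, while this one is meant to assess repeated use over 6 to 12 months.

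Finally, SAP 11 still permits ECG shift tables, and table shells are in a separate document not available here. But the index names the planned tables and includes none for ECG, so the permission leads to no specified output.

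**Conclusion.** The point holds as a gap between endpoint and output. The protocol promises a summary, SAP 4.2 keeps the endpoint, and SAP 11.5 with SAP 17 plans no summary: 0 of 38 tables, against two laboratory shift tables covered by the same general sentence. The SAP conflicts with the protocol and with its own Section 4.2, and SAP 13 does not declare the departure.

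Its size is moderate. No data are lost, no estimate is biased, and shifts can be reconstructed from the listings. What the plan as written does not produce is a count or percentage of treated subjects with a new or worsened ECG finding, or the number with paired readings. The conclusion rests on the index in SAP 17 being the full set of planned tables.

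**What to change.** Add one table to SAP 11.5 and SAP 17: shift in ECG interpretation from baseline to Month 6 and from baseline to Month 12, in the Safety Population.

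- **Categories:** use those the central ECG laboratory supplies. The documents do not state them; the three-level normal/abnormal scale in SAP 11.6 is given for physical examination and should not be assumed for ECG.
- **Denominator:** subjects with both a baseline reading and a reading at that visit, with the number shown.
- **Early termination:** assign these ECGs by the closest-window rule in SAP 6.1 rather than pooling them all with Month 12. A footnote should say whether the windows are built from all visits or only from those with a scheduled ECG, since SAP 6.1 does not say.

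In SAP 11, remove the listing alternative for ECG so that the general text agrees with SAP 4.2 and the protocol. Keep the listings. If the sponsor prefers listings only, SAP 13 should declare that and give the reason, and SAP 4.2 should be reworded to match.

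The cost is a few lines of SAP text and one programmed table from ECGs already scheduled and centrally read. Nothing changes for sites or subjects.
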